Protocol Title: Use of a hyperinsulinemic-hypoglycemic clamp to study hypoglycemia: a method development study.

PI Name: [name]

Sub-Investigator's Name(s): [name], [name], and [name].

Protocol Version Date: November 15th, 2018

Funding: LA CATS/Internal

Objectives

Hypoglycemic complications are a major impediment to the maintenance of healthy glucose levels in persons with diabetes. We recently completed a clinical pilot and feasibility study (GLIMPSE), which identified a novel biomarker that appears to predict the susceptibility to hypoglycemia [1]. By providing an assay to predict hypoglycemic events and therefore diabetic complications, the development of this biomarker could significantly improve the treatment of persons with diabetes.

To pursue such line of research requires the induction and maintenance of hypoglycemia in a controlled safe clinical research setting. A hyperinsulinemic-hypoglycemic clamp is an experimental procedure, which allows for hypoglycemia to be studied in a safe and controlled manner [e.g. 2, 3]. The goal of this study is to establish the hyperinsulinemic-hypoglycemic clamp procedure at Pennington Biomedical Research Center in order to apply the knowledge gained to future studies which will determine the efficacy of our biomarker for predicting susceptibility to hypoglycemia [e.g. aim 2 of the PI's recently funded LA CaTS Roadmap Scholars grant (see appendix A below for project specific aims)]. Additionally, our use of continuous glucose monitoring (CGM) during the clamp procedure will provide novel data regarding the accuracy of CGM during hypoglycemic conditions in a controlled research setting.

Given that the primary purpose of this study is for method development, there is no hypothesis being tested or statistical comparison being made across study participants. We will analyze the time course of the changes in our endpoints in each subject to verify that our procedure produces results that are similar to previously published data from other institutions which have used the hypoglycemic clamp technique. This will allow us to develop an institutional MOP for the hypoglycemic clamp which can be used to safely implement this technique in future studies.

Background

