Although Pennington Biomedical has extensive experience with euglycemic clamp procedures since its introduction by [name] [e.g. 4, 5], experience performing the hypoglycemic clamp procedure is lacking. The procedural differences between the euglycemic clamp and hypoglycemic clamp are minimal. For example, both procedures involve the paired infusion of insulin and glucose, with the rate of glucose infusion being adjusted to achieve a targeted steady-state blood glucose level. In most instances, the

rate of insulin infusion is identical between the two procedures, whereas the rate of glucose infusion differs due to the difference in the targeted blood glucose concentration, which is approximately 100 mg/dL for the euglycemic clamp and 50 mg/dL in the hypoglycemic clamp. Therefore, in order to achieve the lower steady state blood glucose, the initial rate of dextrose infusion during the first 45 minutes of the procedure will be significantly less than the typical rate of dextrose infusion during a euglycemic clamp.

Given our considerable experience with euglycemic clamp and the similarities between the two procedures, we do not anticipate any issues preventing successful implementation of the hypoglycemic clamp procedure. In addition, we have consulted with [name] from the University of Minnesota who has directed multiple studies which utilize this procedure [e.g. 2, 6], to develop the procedure at Pennington (see attached letter of support).

Study Participants

We will enroll up to 8 healthy men or women (goal n=3 completers) in this method development study.

Inclusion and Exclusion Criteria

Inclusion Criteria:

- Healthy male or female
- Ages 18-40 years
- BMI between 20 kg/m² and 30 kg/m² (± 0.5 kg/m² will be accepted)
- Medically cleared for participation in the study

Exclusion Criteria:

- History of clinically diagnosed diabetes or a fasting blood glucose >126 mg/dL
- Average screening blood pressure >140/90 mmHg
- History of cardiovascular disease
- Pregnant, planning to become pregnant, or breastfeeding
- Based on the investigative team's clinical judgement, a subject may not be appropriate for participation in the study.

If eligible, individuals will be enrolled and undergo all testing procedures.

Recruitment Methods

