Given that this is a method development study and we are not comparing across groups or individual participants, a power analysis was not performed.

Data and Specimen Management

Study data collected and entered into the Pennington Biomedical Database is handled only by individuals with appropriate HIPAA compliance and Good Clinical Practice training. Participant charts and hard copy data are stored in locked offices with restricted access. Electronic data has exclusive restricted access granted by the Research Computing Group and/or the PI. For quality control, data and charts will be audited for completeness and accuracy (when possible).

Study data and specimens will be stored indefinitely at Pennington Biomedical in the Clinical Chemistry and [name] Laboratories. Data will be stored with the participant's de-identified ID number. Specimens will be labeled with the participant's de-identified ID number and date of collection. Data and specimens are accessible by the PI, his staff and designated Clinical Chemistry staff in buildings with restricted access

Data analyses: The purpose of this study is to demonstrate proficiency with the hypoglycemic clamp procedure. This will involve demonstrating the ability to achieve and maintain a steady-state blood glucose of approximately 50 mg/dL for approximately 75 minutes and that we are able to measure the known increases in counterregulatory hormone levels associated with exposure to hypoglycemia. This will be indicated by an increase in all four hormones during the steady-state period of the procedure relative to baseline.

Provisions to Monitor the Data to Ensure the Safety of Subjects

We will use the definitions of *Adverse Events*, *Serious Adverse Events*, and *Unanticipated Problems Involving Risks to Subjects or Others* below. Events will be recorded from the participant during their inpatient stay by experienced staff trained in the ascertainment of adverse events from research participants. For each sign, symptom or adverse event, the following information will be recorded:

- A brief descriptor of the adverse event
- Date of onset and date of resolution
- Frequency (single / intermittent)
- Maximum intensity (mild / moderate / severe)
- Outcome (resolved / resolved with sequelae / not resolved)

- Action taken with respect to study drug/intervention (none / dose reduced / temporarily interrupted/ permanently discontinued/ intervention).
- Withdrawal (yes / no)

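### Does the hormone success criterion, a rise in all four hormones, need a stated size, summary and benchmark before it can show that the clamp works?

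*Protocol*

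**What the plan says.** The Data analyses paragraph (under Data and Specimen Management) names two signs of proficiency. The first is glucose held at about 50 mg/dL for about 75 minutes. The second is that "we are able to measure the known increases in counterregulatory hormone levels associated with exposure to hypoglycemia". For the second it adds: "This will be indicated by an increase in all four hormones during the steady-state period of the procedure relative to baseline".

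The Objectives section gives the wider purpose: "We will analyze the time course of the changes in our endpoints in each subject", in order to "verify that our procedure produces results that are similar to previously published data from other institutions". It also states that "there is no hypothesis being tested or statistical comparison being made across study participants".

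The Power analysis section says that "a power analysis was not performed". On size, Study Participants says "We will enroll up to 8 healthy men or women (goal n=3 completers"). Study Endpoints makes blood glucose primary and the four hormones secondary.

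Table 2 schedules ten hormone draws: two at baseline (-15 and 0 min), two while glucose falls (15 and 30 min) and six in the intended steady-state window (45 to 120 min).

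**The concern.** The rule fixes direction only. A 1% rise counts the same as a full counterregulatory response. The text does not say whether the steady-state draws are averaged or the highest is taken, or how many of the three completers must qualify. Different readings behave very differently: one could be met by assay and sampling noise, another could be missed because one of four hormones stayed flat in one person. The rule also contains no published value, although the stated purpose is similarity to published clamps.

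At stake would be the meaning of the hormone result. Meeting the rule might not show that the known response was reproduced, and missing it might not show that the clamp failed. Aim 2 in Appendix A makes this more pointed, because that later work will use the magnitude of the hormone response as its outcome.

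**Working it through.** **Inputs from the protocol.** Four hormones, all required; two baseline draws; up to six steady-state draws; three planned completers. The schedule agrees with itself: 2 + 2 + 6 = 10 draws, and 120 - 45 = 75 minutes. The protocol states no error rate or power for this rule, so there is no figure of that kind to reproduce.

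**Assumptions, not in the protocol.** Draws are normal with equal within-person SD; participants are independent; hormones are independent unless stated; serial correlation is 0, or 0.8 per 15-minute step. Results for correlated draws and for peaks come from simulation with 400,000 runs.

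**No true response.**

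- *Mean steady state against mean baseline.* Each hormone rises with probability 0.5. All four in one participant: 0.5^4 = 6.25%. All three participants: 0.0625^3 = 0.02%. At least one of three: 1 - 0.9375^3 = 17.6%.
- *Same reading, hormones correlated 0.3 or 0.5.* All four in one participant: 14% or 20%. All three participants: 0.14^3 = 0.3% or 0.20^3 = 0.8%.
- *Peak of six against mean baseline.* Per hormone: 0.910 with no serial correlation, 0.762 at 0.8. All four in one participant: 0.910^4 = 69% or 0.762^4 = 34%. All three participants: about 32% or 4%.

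**True response, mean against mean, all four hormones in all three participants (12 checks).** With uncorrelated draws, the difference of means has SD sqrt(1/6 + 1/2) = 0.816 within-person SDs, so the pass probability is Phi(shift/0.816)^12.

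| Rise in every hormone (within-person SDs) | Uncorrelated draws | Serial correlation 0.8 |
|---|---|---|
| 1 | Phi(1.225)^12 = 25% | 12% |
| 2 | Phi(2.449)^12 = 92% | 75% |
| 3 | Phi(3.674)^12 = 99.9% | 98% |

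**True response, stated as an assumed chance q that each hormone shows a rise.**

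| q | All four, one participant (q^4) | All 12 checks (q^12) |
|---|---|---|
| 0.99 | 96% | 89% |
| 0.95 | 81% | 54% |
| 0.90 | 66% | 28% |
| 0.80 | 41% | 7% |

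**Putting the two sides on one basis.** The claim that noise passes easily uses the peak reading per participant (34% to 69%). The claim that a working clamp usually fails uses all three participants at q = 0.90 (28% pass). Judged per participant, that same q gives a 66% pass, so failure is not usual. Judged over all three participants, the peak reading passes on noise in about 4% to 32%, and the mean reading in 0.02%. No single basis yields both faults at the sizes claimed.

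**What a sharper rule could add with three people.** Even if all three completers met any rule, the exact two-sided 95% lower limit for the underlying success rate would be 0.025^(1/3) = 29%. A numerical threshold would not turn the result into strong evidence of reliability.

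**The case for a change.** The best case for a change is that the protocol states the decision rule itself, so the matter is not simply left to an analysis plan. Direction alone does not address similarity to published results. The later project depends on magnitude, and the protocol describes the risk to participants as major, so each clamp should yield an interpretable answer. A few lines and a small table of published values, fixed before the first clamp, would cost little.

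Part of this stands. No minimum rise, summary or required number of completers is written down, and the published-data comparison has no numerical benchmark. If only one completer had to qualify, even the mean reading would pass on noise in 17.6% of studies. If true rises were only about 1 within-person SD, the rule applied to all three would usually be missed.

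The rest is weaker. The unit is not absent: the Objectives section specifies each participant, so a pooled reading fits poorly. The similarity aim is not dropped: the per-participant time-course comparison stands beside the directional check, and nothing says that one replaces the other. The hormones are secondary, and the glucose requirement must also be met, so a noise pass matters only if glucose is held near 50 mg/dL and no hormone responds. Nowhere are 12 of 12 checks demanded, and no document supports a 90% response rate. Reporting the hormones separately instead of jointly is a preference. A useful numerical limit would also have to come from sources outside the protocol, since two baseline draws per person cannot supply it before the first clamp.

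**Conclusion.** No change to the plan follows. The sentence is loosely worded, but its natural reading, mean steady state against mean baseline in each participant, behaves acceptably. Under that reading noise alone passes all three completers with probability 0.02% (below 1% even with hormones correlated 0.5). Rises of 3 within-person SDs pass in 98% to 99.9% of three-person studies.

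These figures rest on assumed normality, variances, correlations and independence between participants. With rises near 1 SD the all-three pass rate falls to between 12% and 25%, and the protocol does not say which size applies. The calculations therefore do not show that the rule passes easily on noise, nor that it usually fails a working clamp.

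What remains is missing definition: the summary, the smallest rise that counts, the number of completers and the published values for comparison. Analysts can settle these when they write up the individual time courses or the procedures manual. They may also be covered in an analysis plan that is not at hand. In a study with three planned completers, no hypothesis test and glucose as the primary endpoint, fixing them in the protocol would not materially change what can be concluded.

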These can be reversed within minutes by stopping the insulin infusion and by raising the blood sugar via increased rate of dextrose infusion. To be certain that the participant's blood sugar level does not drop less than 30 mg/dL, blood glucose will be checked every 5 minutes and adjust as needed. If blood sugar drops too low, seizures or abnormalities in heart rhythm can occur. With careful monitoring, it is very unlikely that the participant's blood glucose will drop to

unsafe levels. In the unlikely event that a participant's blood glucose does drop to less than 30 mg/dL, dextrose will be administered immediately.

The risks of hypoglycemia will be minimized by monitoring the blood glucose every 5 minutes and providing dextrose as needed to achieve the target level of blood glucose. Subjects will also wear a pulse oximeter during the study so we can monitor their heart rate. If we become unable to monitor the glucose during the study or if the participant develops a serious arrhythmia (as defined by the medical staff present), or if blood glucose drops to less than 30 mg/dL, the study will be stopped and dextrose will be given to normalize the blood glucose levels. Medical staff will be present throughout the procedure to monitor the patient. The study will be stopped if the medical staff feels that it is no longer safe for the participant to continue. With careful monitoring, it is very unlikely that a participant's blood glucose will drop to less than 30 mg/dL. If blood glucose drops to less than 35 mg/dL, blood samples will be collected every 3 minutes.

Additional countermeasures to hypoglycemia will also be utilized as necessary.

- **IV Procedure:** There is a possibility of pain, bruising, or infection at the site of the needle insertion for the IV line. Trained personnel also minimize this risk.
- **Questionnaire:** There is a possibility that participants will be uncomfortable answering certain questions. Participants will be told that they may choose to skip any questions.

Potential Benefits to Subjects

There is no direct benefit to participants.

Sharing of Results with Subjects

Results will not be shared with participants.

Setting

This study will be conducted at Pennington Biomedical Research Center in the Outpatient Unit and Inpatient Unit.

Resources Available

Pennington Biomedical Outpatient and Inpatient staff are highly trained individuals with a breadth of experience in clinical research. All have completed human participants protection training and are highly knowledgeable of local study site and culture. A physician is on-call 24 hours a day and is available for consultation or evaluations if necessary. The study regulatory documents will be provided to all staff involved and a startup meeting will be held to ensure all persons assisting with the research are adequately informed about the protocol, the research procedures, and their duties and functions.

Compensation

Participants completing the study visit will receive \$200. No compensation will be provided for screening or run-in visit.

Confidentiality

All data and specimens will be obtained solely for research purposes. These will include 1) physical examinations, 2) medical history, 3) blood samples, and 4) adverse events during study participation. All data from individual participants will be maintained for confidentiality and names and identities will not be disclosed in any published document.

Data will be stored in hard copy in participant charts, which are kept in a locked, secure location only accessible to individuals with human participants protection training. Data will be stored at Pennington Biomedical indefinitely. However, only study investigators, their staff, and collaborators will have access to the data. The study PI is responsible for receipt of the data.

Provisions to Protect the Privacy Interests of Subjects

Provisions to protect privacy interests will be undertaken during this study to ensure participants feel at ease with the research situation. Participants will be continuously reminded they ask any questions or discuss any concerns in private at any time. Examinations, interviews and study procedures will be conducted in private rooms whenever possible.

Compensation for Research-Related Injury

Appendix A- Project specific Aims of the PI's recently funded LA CaTS Roadmaps Scholars grant.

Specific Aims-

Hypoglycemic complications are the major impediment to the maintenance of healthy plasma glucose levels in persons with diabetes. The applicant recently completed a LA CaTS pilot and feasibility project which identified a novel biomarker, glial acetate metabolism, which predicts susceptibility to hypoglycemia. By providing an assay to predict hypoglycemic complications, the development of this biomarker would revolutionize the treatment of persons with diabetes in a manner analogous to the HbA1c assay. This project will build on this initial study to facilitate the applicant's competitiveness for extramural funding of this innovative line of research.

Previous work established that hypoglycemic complications are associated with alterations in glial metabolism. Glia are the most abundant cell type in the brain and play an integral role in cerebral metabolism. Our prior work and that of others has generated three key observations which link alterations in the metabolic capacity of glial cells with

hypoglycemic exposure and hypoglycemic risk: 1) Exposure to hypoglycemia in both diabetic and non-diabetic subjects is associated with an increase in the ability of glial cells to metabolize acetate. 2) This effect is dose-dependent, i.e., greater exposure to hypoglycemia is associated with higher rates of glial acetate metabolism, and 3) Increases in glial acetate metabolism are correlated with acute susceptibility to hypoglycemia in both diabetic and non-diabetic subjects. Based on these observations, we hypothesize that alterations in glial acetate metabolism could be used as an effective biomarker for assessing the risk of hypoglycemic complications in individuals with diabetes.

Securing extramural funding for the appropriate follow-up studies is presently limited due to a lack of preliminary data, the PI's limited experience with clinical research, and the PI's inexperience with key experimental techniques necessary to measure susceptibility to hypoglycemia. The overarching goal of this project is to overcome these limitations while developing fundamental knowledge regarding the relationship between glial metabolism and hypoglycemia. We will achieve this goal through the following specific aims:

Aim 1: Establish the hyperinsulinemic-hypoglycemic clamp procedure at the Pennington Biomedical Clinical Trials Unit (PBRC CTU). This procedure is the gold standard for determining susceptibility to insulin-induced hypoglycemia and therefore is a necessary technique to extend the applicant's preliminary findings and to compete successfully for extramural research support. Establishing this procedure will not only significantly advance the applicants research efforts, but it will also expand the scope of work available to all research projects at the PBRC CTU. The applicant will work with his mentoring team and existing collaborations with key personnel within the PBRC CTU to accomplish this aim.

Aim 2: Determine if glial acetate metabolism predicts future susceptibility to hypoglycemia. We will measure glial acetate metabolism 7 days prior to exposure to insulin-induced hypoglycemia and determine how well this measurement predicts the magnitude of the counter-regulatory responses to a subsequent bout of hypoglycemia. Hypothesis: Glial acetate metabolism will be inversely proportional to the neuroendocrine response to hypoglycemia, that is, as glial acetate metabolism increases the neuroendocrine response will decrease. This aim is a key test of our principal hypothesis. Establishing a link between glial acetate metabolism and future susceptibility to insulin-induced hypoglycemia will significantly advance our initial findings while providing critical preliminary data to support future grant applications.
